Given the serious personal consequences associated with trichotillomania and skin picking disorder, and the likelihood of success of dronabinol in treating both disorders, the aim of the present study was to examine the efficacy and safety of dronabinol vs placebo in adults with trichotillomania or skin picking disorder using a double-blind, placebo-controlled design.

We hypothesize that dronabinol will be more effective than placebo in reducing the frequency of hair pulling and skin picking and in improving overall psychosocial functioning after 10 weeks of treatment when compared to baseline.

Primary Aim/Objective

The aim of the present study is to examine the efficacy and safety of dronabinol vs placebo in adults with trichotillomania and skin picking disorder.

Co-Primary Endpoint(s):

The co-primary efficacy measures will be the change in hair pulling or skin picking frequency and urges to pull hair or pick skin for the past week as indicated by change in total score on the *NIMH Trichotillomania Symptom Severity Scale* (for TTM) or *Skin Picking Symptom Assessment Scale* (for SPD), reliable and valid clinician-administered measures (18-19), as well as the same scale modified for skin picking disorder, and the change in psychosocial functioning over the same time period using the *Sheehan Disability Scale* (20). The co-primary efficacy end points will be the change in these measures from baseline to week 10.

Secondary Aim/Objective

A secondary aim of the study is to examine the effects of dronabinol vs placebo on self-report measures of hair pulling, skin picking, quality of life, and measures of mood and anxiety.

Secondary Endpoint(s):

Secondary efficacy measures include the change in number of days per week pulling, the *Clinical Global Impressions–Improvement Scale* (CGI-I) rated global improvement of symptoms over time (results will be dichotomized as improved [CGI-I ratings of 1 or 2 very much/much improved] or not improved [CGI-I ratings of 3-7]) (20), the self-report *Massachusetts General Hospital Hairpulling Scale* (22), the *Skin Picking Symptom Assessment Scale*, the *Quality of Life Inventory* (23), the *Hamilton Depression Rating Scale* (24), the *Hamilton Anxiety Rating Scale* (25), and the *Tridimensional Personality Questionnaire*

Methodology

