50 individuals with trichotillomania or skin picking disorder will be recruited for a double-blind, placebo-controlled pilot study in which dronabinol or placebo is administered in a 1:1 fashion. All 50 subjects will have trichotillomania or skin picking disorder per DSM-5 criteria. Following baseline measures, all subjects will be randomized to either dronabinol or placebo and seen every 2 weeks for the first four weeks and every 3 weeks for the remainder of the 10-week period.

Participants will be started at 5mg po qday for 2 weeks, then 5mg po bid for 2 weeks and then 5mg TID for the remaining 6 weeks. Participants will only go up to the full dose if clinically needed. Efficacy and safety measures will be performed at each visit.

The study will be conducted in accordance with the International Conference on Harmonization Guideline for Good Clinical Practice, all local ethical and legal requirements, and the World Medical Assembly (Declaration of Helsinki). The study protocol and procedures will be approved by the University of Chicago's institutional review board prior to any recruitment. Written informed consent will be required for study participation.

Randomization of drug will be conducted in blocks of eight. The blind will be assessable to the study subject at all times by calling the pharmacy number listed on the medication bottle. The investigational pharmacy will follow proper accountability procedures in regards to both randomization of the study drug and holding of the blind.

Subjects:

Inclusion criteria:

- 1) men and women age 18-65;
- 2) current DSM-5 trichotillomania or skin picking disorder; and
- 3) Ability to understand and sign the consent form.

Exclusion criteria:

- 1) Unstable medical illness based on history or clinically significant abnormalities on baseline physical examination
- 2) Current pregnancy or lactation, or inadequate contraception in women of childbearing potential
- 3) Subjects considered an immediate suicide risk based on the Columbia Suicide Severity rating Scale (C-SSRS) (www.cssrs.columbia.edu/docs)
- 4) Past 12-month DSM-5 diagnosis of psychosis, major depressive disorder, bipolar disorder, mania, or a substance or alcohol use disorder
- 5) Illegal substance use based on urine toxicology screening
- 6) Stable dose of medications for at least the past 3 months
- 7) Previous treatment with dronabinol

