Although the seizure risk needs to be taken seriously, the occurrence of new seizures from dronabinol, when excluding patients with a seizure disorder, appears to be fairly low even in medically compromised patient (25). In the proposed study, our dose of dronabinol is only up to a total of 15mg each day and patients with trichotillomania are on average quite healthy. This may explain why we saw only a small amount of mild side effects in our previous study (4).

Table 1 outlines adverse events that occurred in subjects with AIDS –related anorexia and chemotherapy-related nausea as well as not medically compromised subjects with trichotillomania (4).

Table 1
Adverse events associated with dronabinol

Adverse event	Pooled trial data from studies of subjects with AIDS-related anorexia and chemotherapy-related nausea ^a	Trichotillomania study participants (n = 14)			
		2.5 mg/day (n = 14)	5 mg/day (n = 13)	10 mg/day (n = 12)	15 mg/day (n = 7)
Light-headed/dizzy	3–10%	2 (14.3%)	1 (7.7%)	1 (8.3%)	–
“High” (i.e., easy laughing, elation, and heightened awareness)	8–24%	–	1 (7.7%)	2 (16.7%)	–
Sedation	3–10%	1 (7.7%)	1 (7.7%)	–	–
Dry mouth	Frequency not specified	–	1 (7.7%)	1 (7.7%)	–
Constipation	Frequency not specified	–	1 (7.7%)	–	–
Headache	<1%	–	–	1 (7.7%)	–
Nausea/vomiting	3–10%	–	1 (7.7%)	–	–
Abdominal pain	3–10%	–	–	–	–
Paranoia	3–10%	–	–	–	–

	Pooled trial data from studies of subjects with AIDS-related anorexia and chemotherapy-related nausea ^a	Trichotillomania study participants (n = 14)			
Any side effect	Frequency not specified	3 (21.4%)	6 (46.2%)	5 (41.7%)	0

^a <http://www.fda.gov/ohrms/dockets/dockets/05n0479/05N-0479-emc0004-04.pdf>

and <http://www.merckmanuals.com/professional/lexicomp/dronabinol.html>

Subject Withdrawal

If a subject withdraws from the study, all instruments administered at the screening visit will be completed at the final visit. These will be conducted when the subject is able to come in for an early termination visit. Withdrawn subjects will be given the phone number of the principal investigator as well as the phone numbers of local resources for trichotillomania and skin picking.

Data and Safety Monitoring Plan

1. Responsibility for Data and Safety Monitoring

The PI will have overall responsibility for monitoring the integrity of study data and participant safety.

2. Procedures for Monitoring Participant Safety

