- Any moderate adverse event which appears definitely, probably, or possibly related to study participation will be reported to the University of Chicago IRB in writing within 20 working days.
- Any mild adverse event will be summarized in the IRB annual progress reports.

Statistical Analysis

Design/Randomization

The study is a double-blind, placebo-controlled study. Participants will be randomized (1:1) to receive dronabinol or placebo by the University of Chicago Investigational pharmacy in block sizes of eight, using computer-generated randomization with no clinical information.

Due to the pandemic of COVID19, study participants can perform their baseline and follow-up visits online using encrypted Zoom instead of in person visits. All inventories will be assessed. Blood samples and urine toxicology, however, will be at the discretion of the study PI. In cases where they are considered medically necessary, the participant can have them drawn locally and submitted to the study team.

Efficacy Analysis

For statistical analysis, the full-analysis set will be defined as all participants who took at least 1 dose of the study drug and had at least 1 post-randomization primary efficacy assessment. The safety-analysis set will be defined as all randomized participants who took at least 1 dose of the study drug and completed at least 1 post-randomization safety assessment. Participants with trichotillomania and skin picking disorder will be grouped as one BFRB group.

We will compare the baseline characteristics of both groups using Fisher's exact test for categorical variables and the t test for continuous variables. We will calculate adherence to treatment, based on the number of pills returned at each visit, as the number of pills taken divided by the number of days in the study $\times 100\%$.

Primary endpoint analysis

The primary outcome measure will be the change from first randomization visit to study endpoint in total composite score on the NIMH Trichotillomania Symptom Severity Scale(s) and the Sheehan Disability Scale.

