The primary analysis of efficacy for continuous measures will be analysis of variance (ANOVA), with terms for treatment to assess differences between treatment groups in the change from first randomization visit to endpoint using the last observation carried forward. The primary analysis for global improvement and response categories will be the Cochran-Mantel-Haenszel test using the last observation carried forward. The primary analysis for $\geq 5\%$ reduction in weight will be Fisher's exact test using the last observation carried forward.

Secondary endpoints analyses

Secondary outcome measures will include the change from first randomization visit to study endpoint in CGI severity and improvement scales, self-reported hair pulling behavior using the MGH-HPS, self-reported skin picking behavior using the SP-SAS, the change in depressive and anxiety symptoms, change in quality of life, and impacts on personality markers. We will use a longitudinal analysis comparing the rate of change of the outcome during the treatment period between groups. The difference in rate of change will be estimated by random regression methods. The model for the mean of the outcome will include terms for treatment, time, and treatment-by-time interaction. To account for the correlation of observations within participants, we will use SAS procedure MIXED with a first-order antedependence covariance structure. The longitudinal analyses will use all available observations from all time points from all participants who completed a randomization visit evaluation.

Safety analyses

We will evaluate differences between groups in the incidence of treatment-emergent adverse events using Fisher's exact test. Descriptive statistics will be used to evaluate changes in laboratory values, blood pressure and heart rate.

Sample Size

The sample size was calculated for the co-primary endpoint of change from randomization. For 80% power to compare the change from randomization, assuming a true effect size of 0.5 between treatment group and the placebo group, 50 participants with a BFRB will be needed in each treatment group based on a 2-group t test at the .05 level of significance. Given the low rates of adverse events expected with dronabinol, we expect few drop-outs from the study and therefore a smaller sample is needed.

Data Management Plan

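### As written, any participant can learn their treatment arm by phoning the pharmacy, with no code-break conditions, recording or analysis handling described

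*Combined protocol and SAP*

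**What the plan says.** The Methodology section, in its paragraph on randomization, says: "The blind will be assessable to the study subject at all times by calling the pharmacy number listed on the medication bottle". The sentence after it reads: "The investigational pharmacy will follow proper accountability procedures in regards to both randomization of the study drug and holding of the blind". These are the only statements on how the blind is kept.

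Under Design/Randomization the protocol declares: "The study is a double-blind, placebo-controlled study".

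The Efficacy Analysis section defines the full-analysis set as "all participants who took at least 1 dose of the study drug and had at least 1 post-randomization primary efficacy assessment". The primary ANOVA compares the groups "in the change from first randomization visit to endpoint using the last observation carried forward". Neither statement mentions participants who have learned their arm.

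The Co-Primary Endpoint(s) section describes the symptom scales, which cover frequency and urges over the past week, as "reliable and valid clinician-administered measures". The secondary aim is to examine "the effects of dronabinol vs placebo on self-report measures of hair pulling, skin picking, quality of life", along with mood and anxiety.

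**The concern.** The access sentence names who may reach the blind (the participant), when (always) and how (a phone call). It sets no condition. A pharmacy that told a caller their arm would be following the protocol, so nothing would mark the disclosure as a deviation.

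The sentence gives no access to raters or analysts, so the gap is on the participant side. Blinded raters do not close it, because a rating of the past week's pulling, picking and urges rests largely on what the participant reports. A participant who knows the arm and stays in the trial may report symptoms, disability and quality of life in line with expectation. One who learns they are on placebo may leave early, and last observation carried forward then makes an early score the endpoint. No count of such calls is planned, so a reader of the results may be unable to tell how often this happened.

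**Working it through.** **Text check.** The plan states no figure on unblinding, so there is none to reproduce. The first step is to see whether any other text limits the access sentence.

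| Place | What it provides | Limits participant access? |
|---|---|---|
| Methodology, sentence after the access sentence | General assurance on accountability and holding the blind; may imply some record | No |
| Safety Assessments (including seizures) | Discontinuation and contact with a healthcare provider; unblinding not mentioned | No |
| Subject Withdrawal | Final-visit instruments and contact numbers | No |
| Monitoring Committee; Reporting Adverse Events | Yearly review, record audit, adverse event reporting | No |
| Design/Randomization | 1:1, blocks of eight, run by the pharmacy | No |
| Efficacy Analysis; primary, secondary and safety analyses | Analysis sets, ANOVA with LOCF, mixed model, Fisher's exact test | No |
| Methodology and Ethical Considerations, GCP statements | General commitment to standards | No |

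No text says when the code may be broken, who authorises it, what is recorded, or how ratings made after unblinding are treated.

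**Size, by assumption.** Inputs from the documents: 50 participants randomized 1:1, so n = 25 per arm (Methodology); a two-group t test at the .05 level and an assumed effect size of 0.5 (Sample Size). The test is taken as two-sided, which the protocol does not state. Assumed here: no true effect; a share *p* of each arm calls; and the total gap between arms among callers is *g* SD, fully present in the endpoint rating.

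- Spurious difference: δ = p × g.
- Noncentrality: λ = δ × √(n/2) = δ × √12.5 = 3.536 × δ.
- Two-sided rejection rate: P(|T| > 2.011), where T is noncentral t with 48 df and noncentrality λ.

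| p | g (SD) | δ (SD) | λ | False-positive rate | Part falsely favouring dronabinol (nominal 2.5%) |
|---|---|---|---|---|---|
| 4% (1 of 25) | 0.5 | 0.02 | 0.071 | 5.1% | 2.9% |
| 10% | 0.5 | 0.05 | 0.177 | 5.3% | 3.7% |
| 10% | 1.0 | 0.10 | 0.354 | 6.4% | 5.3% |
| 20% | 0.5 | 0.10 | 0.354 | 6.4% | 5.3% |
| 20% | 1.0 | 0.20 | 0.707 | 10.7% | 10.3% |

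In the last row the spurious difference is 0.20/0.5 = 40% of the assumed effect. A simulation with a random number of callers (400,000 trials per case) gave 5.3%, 6.3% and 10.4% for 10%/0.5 SD, 10%/1.0 SD and 20%/1.0 SD, close to the formula.

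The Sample Size section speaks of 50 per group. With that size, differences of 0.05, 0.10 and 0.20 SD give 5.7%, 7.9% and 16.8%. These do not describe the planned trial of 50 in total.

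**The case against.** The access sentence is plainly faulty, and once its wording is doubted it is weak evidence of a deliberate policy of disclosure on request. A round-the-clock safety line printed on the bottle is at least as plausible. The seizure text under Safety Assessments gives such a line a purpose, and the pharmacy is told to hold the blind. The protocol also commits to GCP and sets up an independent committee that audits records. Pharmacy instructions and consent wording are not in the material reviewed and may contain a procedure. The size is entirely assumed: four of the five scenarios give 5.1% to 6.4% against a nominal 5%, and the rate doubles only if a fifth of each arm calls and the gap among callers is twice the trial's assumed effect.

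Much of this stands. Emergency access may well have been the intention, the practical harm may be negligible, and 10.7% is the extreme of the cases examined. It does not remove the point. The text names the participant and sets no limit on timing or reason, and none of the general assurances restricts that. If only an emergency line was meant, the protocol should say so.

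It could also be said that the permitted reasons for breaking the code are for the sponsor to set. A release rule is a blinding procedure, however, and changes no dose, treatment or stopping rule.

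**Conclusion.** The concern holds as a conflict between an operative instruction and the declared double-blind design. That rests on reading *assessable* as *accessible*, and on the protocol and analysis text alone. How often the line would be used is unknown.

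Under the assumptions shown, the effect on the false-positive rate runs from negligible (5.1%) to about double the nominal 5% (10.7%) in the extreme case. The calculation does not model early departure by participants who learn they are on placebo, which the documents neither support nor exclude.

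Only part of the blinding risk comes from this sentence. Table 1 records feeling high ("easy laughing, elation, and heightened awareness") in 1 of 13 participants at 5 mg/day, 2 of 12 at 10 mg/day and none of 7 at 15 mg/day in the earlier open-label study, so some may guess their arm whatever the pharmacy does. The change should be made, because it is cheap and the outcomes depend on the participant's account.

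**What to change.** Replace the access sentence in Methodology with wording along these lines:

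> The pharmacy number on the bottle is for emergencies. The assignment is released only for a medical emergency or safety need, through the investigator or a treating clinician, and not to the participant on request. The pharmacy records the date, the reason and the persons informed. Raters and analysts stay blinded. Participants are otherwise told their arm after database lock.

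In the analysis section, state that unblinded participants stay in the full-analysis set and that the number unblinded is reported by arm. Any analysis that excludes ratings made after unblinding should be supportive only. It may be selective if calling differs by arm, and under the planned LOCF it would carry earlier scores forward.

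The cost is a few sentences plus matching pharmacy instructions and consent wording. Participants lose on-demand access to their assignment, while emergency access is kept. The change does not prevent guessing from drug effects.

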Pathological hair-pulling, trichotillomania, has been defined as repetitive, intentionally performed pulling that causes noticeable hair loss and results in clinically significant distress or functional impairment (1). Although discussed in the medical literature for over one hundred years, and affecting all strata of society, there have been no epidemiological studies detailing how common trichotillomania is and there are no clear treatment approaches for everyone with trichotillomania. Behavioral therapy is generally regarded as the first-line treatment but trained therapists are difficult to find. In addition, there is no medication currently approved by the Food and Drug Administration for trichotillomania. Trichotillomania is related clinically to other BFRBs, specifically skin picking disorder. In fact, it appears that trichotillomania and skin picking disorder may in fact share a common neurobiology. Other BFRBs such as skin picking disorder also lack any agreed upon medication intervention, but evidence suggests that both skin picking disorder and trichotillomania may respond to the same interventions.

The Trichotillomania Impact Project survey showed that only 15% of adults in the community with trichotillomania reported experiencing significant improvement with treatment of their symptoms (2). This may be because of the ongoing difficulty of finding a therapist

experienced in trichotillomania treatments. More than 55% of persons in this survey believed that their clinician did not have sufficient knowledge of the disorder, and less than one-third were receiving evidence-based treatments for trichotillomania (2).

A recent meta-analytic study of randomized treatment trials in adults demonstrated that behavioral treatments, mainly habit reversal therapy, have the greatest efficacy in treatment of trichotillomania and skin picking disorder (3). Selective serotonin reuptake inhibitors (SSRIs) are the most widely used treatment for adults with trichotillomania and skin picking disorder, despite evidence that their efficacy is no greater than placebo (3).

Instead of using SSRIs, we conducted an open-label study of dronabinol a synthetic form of tetrahydrocannabinol (THC) approved by the FDA as an appetite stimulant for people with AIDS and antiemetic for people receiving chemotherapy, in 14 women with trichotillomania and found that 9 (64.3%) responded to treatment and that the mean effective dose was 11.6 ± 4.1 mg/day (4).

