- 8) Cognitive impairment that interferes with the capacity to understand and self-administer medication or provide written informed consent

Baseline Assessments:

Those subjects who appear appropriate for the study, based on telephone screening, will be invited for a baseline assessment. The duration of the baseline assessment will be approximately 90 minutes and will include the following: informed consent, demographic data, concomitant medications (no psychotropic medications will be allowed), and family history data. There will also be a physical examination (including weight, and vital signs, urine pregnancy test for women of childbearing years and urine drug screen, as well as a baseline blood draw to assess nutritional status. The blood draw is optional to the subject and will administered at the PI's discretion). Finally, the subjects will undergo a psychiatric evaluation (using the MINI International Neuropsychiatric Interview).

In addition, the following instruments will be completed at the screening visit: 1) NIMH Trichotillomania Symptom Severity Scale (or the same scale modified for skin picking); 2) Sheehan Disability Scale; 3) Massachusetts General Hospital Hairpulling Scale; 4) the 17-item

Hamilton Rating Scale for Depression (HAM-D); 5) the 17-item Hamilton Rating Scale for Anxiety (HAM-A); 6) Clinical Global Impression (Improvement and Severity) scale; 7) Cambridge Caffeine Use Questionnaire; 8) The Dietary Fat and Free Sugar Questionnaire and 9) the Quality of Life Inventory; 10) Cambridge-Chicago Trait Scale (12); the Skin Picking Symptom Assessment Scale (SP-SAS); and the Body Focused Repetitive Behavior Broad Assessment Measure (BFRB-BAM), a new scale being added for validation purposes. In addition, subjects will undergo cognitive assessments at baseline and study endpoint.

Cognitive Assessments: Assessments of cognitive control will be comprised of several valid paradigms (See below). These tasks are designed to probe dissociable neural circuitry and cognitive processes likely to be implicated in the pathophysiology of addictions. Task order was chosen arbitrarily and will be applied consistently across subjects, to minimize possible confounding factors of differences in task order across participants.

The following tasks will be administered at baseline and final visits:

- Stop Signal Task of Inhibitory Control (SST)
- Intra-dimensional/Extra-dimensional Set Shift Task (ID/ED task)
- One Touch Stockings Task (OTS)

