- Rapid Visual Processing Task (RVP)
- Spatial Working Memory Task (SWM)
- Cambridge Gambling Task (CGT)

Following-Up Visit Assessments

All follow-up visits will include all psychiatric measures (except the MINI which will be done at baseline only) and safety measures (adverse events, vital signs, C-SSRS). There will be four follow up visits for a total of five visits.

Subject Compensation

Subjects will be compensated \$20 per visit, for a total of \$100. Compensation will be given in the form of a check at the end of the study, as per University of Chicago protocol.

Safety Assessments

Safety and tolerability will be assessed using spontaneously reported adverse events data, Columbia–Suicide Severity Rating Scale (C-SSRS), vital signs, and by evaluating premature termination. Safety assessments (C-SSRS, sitting blood pressure, heart rate, adverse effects, and concomitant medications) will be documented at each visit. Subjects who are an immediate suicide risk will be removed from the study and appropriate clinical intervention (e.g. hospitalization) will be arranged. Urine pregnancy tests will be performed at the initial visit. Subjects who have a positive urine pregnancy test will be excluded from the study. Assessment of side effects will be done at each visit. AEs will be coded by system organ class (SOC) and preferred term (PT) using the Medical Dictionary for Regulatory Activities (Med- DRA) Version 11.1. The incidences of all AEs will be summarized descriptively. In terms of vital signs, those subjects with abnormal blood pressures will be assessed for symptoms of hypo- or hypertension. Asymptomatic subjects will be evaluated each visit for changes in vital signs. In the case of hypertensive emergencies (BP greater than 210/120), appropriate referral to the emergency room will be made. In the case of hypotension (BP less than 90/60), participants will be evaluated for symptoms of hypotension and if symptomatic, appropriate interventions will be made.

Seizure and seizure-like activity have been reported in patients receiving dronabinol. Therefore, history of seizures will be an exclusion criterion. If a seizure occurs, dronabinol will be discontinued. Participants will be advised to discontinue dronabinol and contact a healthcare provider immediately if they experience a seizure.

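### Pregnancy is tested for only at the initial visit: no retest, contraception re-check or on-treatment stopping rule during 10 weeks of dosing, and no stated method for a remote baseline (minor)

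*Combined protocol and SAP*

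**What the plan says.** The exclusion criteria bar "Current pregnancy or lactation, or inadequate contraception in women of childbearing potential". The test appears in two places, both at entry. Baseline Assessments includes a "urine pregnancy test for women of childbearing years and urine drug screen" in the physical examination, and Safety Assessments states "Urine pregnancy tests will be performed at the initial visit". Safety Assessments adds that a positive result leads to exclusion, without naming a visit.

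After baseline, participants are "seen every 2 weeks for the first four weeks and every 3 weeks for the remainder of the 10-week period". Following-Up Visit Assessments gives the content of those visits as the psychiatric scales plus "safety measures (adverse events, vital signs, C-SSRS". The per-visit list in Safety Assessments covers the C-SSRS, blood pressure, heart rate, "adverse effects, and concomitant medications) will be documented at each visit". Neither list has a pregnancy test.

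Subject Withdrawal repeats the screening instruments at an early final visit. The COVID-19 text under Design/Randomization lets baseline and follow-up visits be held online. It leaves blood samples and urine toxicology to the PI's discretion and allows local collection when medically necessary; it does not name pregnancy tests.

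**The concern.** By its own exclusion criteria the plan treats pregnancy as disqualifying, yet it looks for pregnancy on a schedule only once. A pregnancy too early to show at baseline, or one conceived on treatment, would come to light only through participant report or clinical suspicion.

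Until then dosing could continue and rise. The Methodology schedule moves from 5 mg once daily to 5 mg twice daily after week 2, and to 5 mg three times daily after week 4, with the qualification "Participants will only go up to the full dose if clinically needed".

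Two other risks are handled differently. Immediate suicide risk is excluded at entry, re-checked by C-SSRS at every visit, and leads to removal. Seizure history is excluded, and a seizure on treatment stops dronabinol. Pregnancy has neither a scheduled re-check nor an explicit on-treatment stopping rule.

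**Working it through.** **Visit schedule.** Every 2 weeks to week 4 and then every 3 weeks to week 10 gives visits at weeks 2, 4, 7 and 10. That is four follow-up visits plus baseline, five in all, as Following-Up Visit Assessments states. It also agrees with Subject Compensation: 5 × $20 = $100.

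**Scheduled pregnancy tests.** There is one in five visits, at baseline, and none at weeks 2, 4, 7 or 10. Three places might have held a repeat:

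- Methodology promises safety measures at each visit, but the two later lists define these without a pregnancy test.
- Subject Withdrawal repeats instruments. Baseline Assessments uses that word for rating scales and questionnaires, and lists the pregnancy test separately under the physical examination.
- The remote-visit text covers inventories, blood samples and urine toxicology. Urine toxicology is not a pregnancy test.

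**Inputs for the size.**

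- From the documents: 50 participants in total (Population, Methodology), randomized 1:1; female-to-male ratio about 3:1 (Data Management Plan); 10 weeks of dosing.
- Assumed: a conception becomes detectable after 2 weeks; pregnancy rates of 1%, 3% or 10% per year. The documents give neither figure.

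**Women.** 0.75 × 50 = 37.5 in the trial; 37.5 / 2 = 18.75 on dronabinol.

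**Window in which retesting can shorten exposure.** Conceptions before week −2 would show at baseline. With a 2-week lag, those up to week 5 would show by week 7. Later ones first show at week 10, when dosing ends. The window is therefore week −2 to week 5, which is 7 weeks.

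**Expected number on dronabinol** = annual rate × women × 7/52.

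| Women on dronabinol | Woman-years | 1% | 3% | 10% |
|---|---|---|---|---|
| 18.75 (3:1, all of childbearing potential) | 18.75 × 7/52 = 2.52 | 0.025 | 0.076 | 0.25 |
| 11.25 (60% of these, assumed) | 11.25 × 7/52 = 1.51 | 0.015 | 0.045 | 0.15 |

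**Intervals.** The longest stretch of dosing with no scheduled test is now 10 weeks. With tests at weeks 2, 4 and 7 the gaps are 2, 2 and 3 weeks, with 3 more to the end of dosing, so the longest is 3. Undetected exposure can last longer. A conception just after week 2 is missed at week 4 and found at week 7, which is 2 + 3 = 5 weeks.

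**Tests.** Blinding means that both arms are tested. Three visits: 37.5 × 3 = 112.5, about 113. With week 10: 37.5 × 4 = 150.

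**The case against.** The strongest reply is that retest frequency is a judgement, and that the plan already has safeguards. Contraception is screened at entry, adverse effects and concomitant medications are recorded at each visit, and the PI evaluates safety at each visit (Data Management Plan). The remote text offers local collection at the PI's discretion. No section promises a second test. The documents give no data on dronabinol in pregnancy, so the size of any harm cannot be judged from them. The consent pages are not in the reviewed text and may carry instructions on contraception or stopping.

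Most of this stands, and it keeps the point minor. It does not close the gap: these safeguards lower the risk or allow chance detection, but none is a scheduled check. The local-collection route covers blood samples and urine toxicology. The exclusion sentence names no visit, but the only scheduled test it can act on is the initial one.

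A reader might infer a larger problem by counting every conception in the trial during weeks 0 to 10: 37.5 × 10/52 = 7.21 woman-years, or 0.07, 0.22 and 0.72 at the same assumed rates. Those figures do not measure what retesting could achieve. Half fall on placebo, and conceptions after week 5 are detectable only when dosing ends. The 10% rate also has no support in the documents for women screened for adequate contraception.

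**Conclusion.** The point holds as a minor, inexpensive improvement in participant safety. The visible text has one scheduled pregnancy test, no later contraception check, no explicit stopping rule for pregnancy on treatment, and no method for the entry test at an online baseline.

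The expected benefit is small: about 0.025 to 0.25 conceptions on dronabinol whose exposure could be shortened, and fewer if some of the women are not of childbearing potential. This rests on the assumed 2-week lag, the assumed annual rates, and a 3:1 ratio that the plan gives as an estimate for the disorders and not as an enrolment quota.

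A reader might go further and call this an internal contradiction, or take the remote-visit text as waiving the entry test. The documents support neither. The plan never commits to retesting, and the remote text is silent on pregnancy tests. Efficacy, power and error rates are unaffected.

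**What to change.** For women of childbearing potential:

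- Add a urine pregnancy test and a brief contraception check to the follow-up safety measures at weeks 2, 4 and 7, completed before any dose increase. Week 7 belongs in the schedule because weeks 4 to 10 are the longest phase and the one at the highest planned dose.
- Treat a test at week 10 or early termination as optional. It documents exposure but cannot prevent it.
- Require a home or local test for every remote visit, including a remote baseline before the first dose.
- State that study drug stops on a positive test at any visit.

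**Cost.** About 113 extra urine tests at 3:1, or about 150 with week 10. If 60% of the women are of childbearing potential (assumed), this is 22.5 × 3 = 67.5, about 68, or 22.5 × 4 = 90 with week 10. If every visit were remote, baseline plus three follow-ups would need 37.5 × 4 = 150 kits, sent out and read with staff. The rest is a few minutes per visit and a few lines of protocol text. The documents give no unit price. No added visit, sample-size change or analysis change is needed.
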